7.13.3. Analyses of Vital Signs and Weight

Vital sign measurements (including weight) will be analyzed using continuous data (change from baseline) and categorical data (proportion of treatment-emergent abnormalities).

If there are multiple records of vital sign or weight measurements at baseline or post-baseline visit(s), the last record will be used.

The analyses will be done for the following vital sign measurements and weight:

- systolic blood pressure
- diastolic blood pressure
- pulse
- temperature, and

- weight.

7.13.3.1. Analyses of Continuous Data

Change from baseline to each post-baseline visit at which the vital signs are taken will be assessed using an ANCOVA model with treatment as independent factors and baseline value and age as covariate in the model. This analysis will be done separately for each vital sign parameter and weight.

7.13.3.2. Analyses of Categorical Data

Treatment differences in the proportion of participants with treatment-emergent high, treatment-emergent low or treatment-emergent abnormal vital sign measurement will be assessed between treatment groups using Fisher's exact test at (1) anytime (2) each post-baseline visit.

Treatment-emergent high vital sign measurements are the values which are low or normal at the baseline visit and fall into the high category at post-baseline visit(s). Similarly, treatment-emergent low vital sign measurements are the values which are high or normal at the baseline visit and fall into the low category at post-baseline visit(s). Treatment-emergent abnormal vital sign measurements are the values which are normal at the baseline visit and fall into the high or low category at post-baseline visit(s). The criteria for post-baseline low and post-baseline high are provided in [Table A4.SAP.4](#).

For each vital sign at each postbaseline visit, only participants who had a baseline result and had a non-missing result at that postbaseline visit will be included in the denominator when computing the proportion of participants with treatment-emergent high, low, or abnormal values.

Summary and analyses of change from baseline in weight will be provided. The proportion of participants with a weight gain or loss of greater than or equal to 4 percent of baseline body weight will be compared between treatment groups using Fisher's exact test at each visit and at any time. In addition, categories of BMI (underweight = < 18.5 , normal = $\geq 18.5 - < 25$, overweight = ≥ 25 to < 30 , obese = ≥ 30) will be compared between treatment groups using Fisher's exact test at (1) anytime and (2) each post-baseline visit.

Table A4.SAP.4. Criteria for Abnormal Vital Signs and Weight

Vital Sign Parameter (Unit)	Postbaseline Low Criteria	Postbaseline High Criteria
Systolic Blood Pressure (mmHg)	Absolute value ≤ 90 and ≥ 20 decrease from baseline	Absolute value ≥ 160 and ≥ 20 increase from baseline
Diastolic Blood Pressure (mmHg)	Absolute value ≤ 50 and ≥ 10 decrease from baseline	Absolute value ≥ 100 and ≥ 10 increase from baseline
Pulse (bpm)	Absolute value < 50 and ≥ 15 decrease from baseline	Absolute value > 100 and ≥ 15 increase from baseline
Weight	$\geq 4\%$ decrease	$\geq 4\%$ increase
Vital Sign Parameter	Postbaseline Criteria for Abnormality	
Temperature	Absolute value $\geq 38.3^{\circ}\text{C}$ and $\geq 1.1^{\circ}\text{C}$ increase from baseline (Absolute value $\geq 101^{\circ}\text{F}$ and $\geq 2^{\circ}\text{F}$ increase from baseline)	

Abbreviation: bpm=beats per minute.

7.13.4. Analyses of Electrocardiograms

Electrocardiogram (ECG) measurements will be analyzed using continuous data (change from baseline) and categorical data (proportion of treatment-emergent abnormalities).

Since ECG is measured in triplicates, the average of triplicates will be used for baseline and postbaseline visit(s). If there are multiple records after averaging ECG triplicates within a visit, the last record of averages will be used.

The analyses will be done for the following ECG measurements:

- heart rate
- PR interval
- QRS duration
- QT interval, and
- QTc interval.

All analyses of QTc will be carried out using the Fridericia correction (QTcF) method. These summaries will include data from each visit at which ECG measures are performed.

7.13.4.1. Analyses of Continuous Data

Change from baseline to each postbaseline visit at which ECG measurements are taken will be assessed using an ANCOVA model. The model for the fixed effects will include terms for the following independent effects: baseline ECG score, treatment. This analysis will be done separately for each ECG parameter.

7.13.4.2. Analyses of Categorical Data

Incidence of treatment-emergent abnormal ECGs will be compared between treatment groups by Fisher's exact test at (1) anytime and (2) each post-baseline visit.

Abnormal ECG criteria are presented in [Table A4.SAP.5](#) and criteria for abnormal QTcF prolongation are presented in [Table A4.SAP.6](#).

Table A4.SAP.5. Criteria for Abnormal ECG Parameters

ECG Parameter	Low Criteria	High Criteria
Heart Rate	≤ 40 bpm	≥ 120 bpm
PR Interval	≤ 120 msec	≥ 220 msec
QT Interval		> 500 msec
QRS Duration	< 60 msec	≥ 120 msec

Abbreviations: bpm = beats per minute; ECG = electrocardiogram; msec = millisecond.

Table A4.SAP.6. Criteria for Identifying Participants with a Prolonged ECG QTcF Interval

Criterion Number	Criterion
1	In adult males, QTcF > 450 msec; in adult females, QTcF > 470 msec
2	QTcF ≥ 500 msec
3	Increase of > 0 msec and ≤ 30 msec relative to baseline
4	Increase of > 30 msec and ≤ 60 msec relative to baseline
5	Increase of > 60 msec relative to baseline
6	Increase of > 60 msec relative to baseline and QTcF ≥ 500 msec

Abbreviations: ECG = electrocardiogram; msec = millisecond; QTcF = Fridericia's corrected QT interval.

Treatment-emergent high ECG parameters (heart rate, PR interval, QRS duration, QT and QTcF intervals) are the values which are low or normal at the baseline visit and fall into the high abnormal categories at post-baseline visit(s) in [Table A4.SAP.5](#) and [Table A4.SAP.6](#) postbaseline. Similarly, treatment-emergent low ECG parameters (heart rate, PR interval, QRS duration) are the values which are high or normal at the baseline visit and fall into the low abnormal categories at postbaseline visit(s) above.

7.13.5. Analyses of MRI Data

To evaluate any changes in MRI data following treatment, Fisher's exact test will be used to compare frequencies of responses in the MRI parameters.

Frequencies and percentages of the following amyloid-related imaging abnormality – edema (ARIA-E, also known as vasogenic edema) and ARIA – hemorrhage (ARIA-H

, also known as microhemorrhage) parameters will be summarized:

- ARIA-E:
 - Status compared to the previous MRI(s) (increased, unchanged, partial resolution, or complete resolution)
 - ARIA-E by APOE4 genotype
- ARIA-H:
 - Number of ARIA-H (≤4, 5–10, >10, or no presence),
 - Presence of superficial siderosis,

- Baseline to each visit (at which MRI is done) changes (increase in size of pre-existing ARIA-H, increase in number of ARIA-H, no change, partial resolution, or complete resolution), and
- ARIA-H by APOE4 genotype.

To investigate the effect of dose increases on MRI safety parameters, ARIA-E and ARIA-H rates for the first MRI subsequent to the dose increase will be displayed.

7.13.5.1. Analysis of MRI Data by Dose

For participants treated with solanezumab, summaries of ARIA-E and ARIA-H events will be displayed with events assigned to the dose (400 mg versus 1600 mg for participants assigned to solanezumab, with events occurring at the 800-mg level assigned to the 1600-mg group, and low-dose placebo and high-dose placebo for participants assigned to placebo based on the blinded dose level) that the participant was taking at the time of the event. At the first occurrence of a high dose for a participant, all subsequent observations will also be considered as high dose.

7.13.6. Analyses of Immunogenicity Data

7.13.6.1. Immunogenicity Definitions

[Figure A4.SAP.2](#) provides an overview of the immunogenicity assay process. At a high level, an individual sample is potentially examined multiple times, in a hierarchical procedure, to produce a sample solanezumab ADA assay result and potentially a sample solanezumab neutralizing antibody (NAb) assay result. The drug tolerance of each assay, the possible values of titers, and the cutpoints applied are operating characteristics of the assays and the hierarchical testing procedure of [Figure A4.SAP.2](#).

It can be the case that the presence of high concentrations of solanezumab will affect the measurements of the presence of ADA or NAb, and conversely high levels of ADA or NAb may affect the measurement of LY concentration. Thus an LY drug concentration, assessed from a sample drawn at the same time as the ADA sample, plays a key role in clinical interpretation of a sample when the laboratory result is Not Detected, as shown in [Figure A4.SAP.2](#).

The rest of this section defines the component concepts of [Figure A4.SAP.2](#) in greater detail.

[figure not shown]

Figure A4.SAP.2. Flow Chart of ADA Assessment with Clinical Interpretation of the Various Result Possibilities

Abbreviations: ADA = anti-drug antibody; NAb = neutralizing antibody; PK = pharmacokinetic.

Definitions of ADA statuses (Table A4.SAP.7) and clinical interpretation results (Table A4.SAP.8) are provided below.

Table A4.SAP.7. Sample ADA Assay Results

Sample Laboratory Result	Explanation
Detected	ADA are detected and confirmed.
Not Detected	The raw result as reported from the laboratory indicates ADA not detected. The clinical interpretation of such results depends on other factors (see below).
NO TEST, QNS (quantity not sufficient), etc.	Sample exists but was un-evaluable by the assay

Abbreviation: ADA = anti-drug antibody.

Table A4.SAP.8. Sample Clinical ADA Interpretation Results

Sample Clinical Interpretation	Explanation
ADA Present	ADA assay result is Detected
ADA Not Present	ADA assay result is Not Detected and simultaneous drug concentration is at a level that has been demonstrated to not interfere in the ADA detection method (i.e., drug concentration is below the assay's drug tolerance level). If drug concentration is not available for a treatment-period sample, the sample is inconclusive (see below). For pre-treatment samples and participants receiving placebo, drug concentration is not assessed and is assumed to be below the assay's drug tolerance level.
ADA Not Detected, Drug Concentration Not Available	If drug concentration is expected per protocol but not available, the immunogenicity sample is "ADA Not Detected, Drug Concentration Not Available" for the purpose of participant listings. For the purpose of TE ADA computation (see below), these samples are taken to be ADA Not Present.
ADA Inconclusive	ADA assay result is Not Detected but drug concentration in the sample is at a level that can cause interference in the ADA detection method, or drug concentration is planned per protocol but is not available.
ADA Missing	ADA sample not drawn, QNS, not tested, etc., causing there to be no laboratory result reported or the result is reported as "no test".

Abbreviations: ADA = anti-drug antibody; TE = treatment-emergent; QNS = quantity not sufficient.

Parallel terminology applies for Neutralizing ADA (NAb) Detected, NAb Not Detected, NAb Present, NAb Not Present, NAb Inconclusive, NAb Missing. Anti-drug antibodies and Neutralizing ADA (NAb) are distinct assays and have different assay operating characteristics.

A post-baseline immunogenicity sample with ADA Present is said to have TE ADA titer if the titer meets the criteria to classify the participant as TE ADA+.

7.13.6.1.1. Definitions of Immunogenicity Assessment Periods

- **Immunogenicity Baseline Observations:** Baseline period for immunogenicity assessment for each participant includes all observations on or prior to the date of the first administration of study drug. In instances where multiple baseline observations are collected, to determine participant ADA status the lowest titer/not detected is used to determine treatment-emergent status (see below).
- **Immunogenicity Post-baseline Period Observations:** Post-baseline period observations for each participant includes all observations after the first administration of study drug.

7.13.6.1.2. Definitions of Participant ADA Status

- **Participant evaluable for treatment-emergent ADA:** A participant is evaluable for TE ADA if the participant has a non-missing baseline ADA result, and at least one non-missing post-baseline ADA result.
- **Treatment-emergent ADA positive (TE ADA+) participant:** A participant who is evaluable for TE ADA is treatment-emergent ADA positive (TE ADA+) if either of the following holds:
 - a. The participant has baseline status of ADA Not Present and at least one post-baseline status of ADA Present with titer $\geq 2 \times$ MRD, where the MRD is the minimum required dilution of the ADA assay.
 - b. The participant has baseline and post-baseline status of ADA Present, with the post-baseline titer being 2 dilutions (4-fold) greater than the baseline titer. That is, the participant has baseline status of ADA Present, with titer 1:B, and at least one post-baseline status of ADA Present, with titer 1:P, with $P/B \geq 4$.
- **Treatment-emergent ADA Inconclusive participant:** A participant who is evaluable for TE ADA is TE ADA Inconclusive if $\geq 20\%$ of the participant's post-baseline samples, drawn pre-dose, are ADA Inconclusive and all remaining post-baseline samples are ADA Not Present.
- **Treatment-emergent ADA negative (TE ADA-) participant:** A participant who is evaluable for TE ADA is TE ADA negative (TE ADA-) when the participant is not TE ADA+ and the participant is not TE ADA Inconclusive.

7.13.6.2. Immunogenicity Statistical Analyses

A listing will be provided of all immunogenicity assessments for those participants who at any time had ADA Present. This includes the laboratory ADA assay result (Detected or Not Detected), solanezumab concentration from a simultaneous pharmacokinetic sample, and the clinical interpretation result that combines these (ADA Present, ADA Not Present, ADA Inconclusive, Missing). When Detected, a titer will be included, and TE ADA+ observations will be flagged. Also included, when the NAb assay was performed, will be the laboratory NAb assay result (Detected or Not Detected) and the NAb clinical interpretation result (NAb Present, NAb Not Present, NAb Inconclusive, Missing).

For the remainder of this section, mention of ADA result and NAb result will refer to the respective clinical interpretation result.

The number and proportion of participants who are TE ADA+ will be tabulated by treatment group, where proportions are relative to the number of participants who are TE ADA evaluable, as defined above. This analysis will include all post-baseline observations and will examine solanezumab ADA and solanezumab NAb. The tabulation will include the number and proportion of participants with ADA Present at baseline, and also the number and proportion of TE ADA+ participants exhibiting NAb+. For analysis sets involving both solanezumab and placebo, results between solanezumab and placebo-treated groups will be compared using a Cochran-Mantel-Haenszel test stratified by study, for TE ADA+ and for TE ADA+ with NAb+.

A summary will be provided of the number and percentage of solanezumab-treated participants experiencing TEAE (overall and by PT) by participant TE ADA status (TE ADA+, TE ADA-, TE ADA Inconclusive). The PT will be ordered by decreasing incidence in TE ADA+ status group.

In order to assess the clinical relevance of TE immunogenicity, specific acute and non-acute AEs will be evaluated. A listing will be provided of these events for all participants who were TE ADA+. This listing includes a time course of ADA (clinical interpretation result, plus flags for samples with TE ADA titer or NAb+ samples) along with the AE. Listings with the same structure will be provided of (i) these events of interest for participants who had ADA Present at any time (including baseline) but who were not TE ADA+, and (ii) all TEAE for TE ADA+ participants.

The time from first dose to the first TE ADA titer will be summarized cumulatively for representative time intervals over the course of the study.

Sample clinical interpretation result, represented as ADA Not Present, ADA Inconclusive, or as a titer value for ADA Present samples, will be displayed in a shift table from baseline to maximum post-baseline. For participants with a post-baseline ADA Present sample, the maximum post-baseline value is the maximum titer observed at any time post-baseline. For participants without a post-baseline ADA Present sample, the maximum value is ADA Inconclusive, if such a result was observed. If no participants had maximum value of ADA Inconclusive, then ADA Inconclusive will not be displayed in the table.

7.13.7. Analyses of Additional Safety Data

7.13.7.1. Columbia-Suicide Severity Rating Scale

Suicidal ideation, suicidal behavior, and self-injurious behavior without suicidal intent, based on the Columbia-Suicide Severity Rating Scale (C-SSRS), will be listed by participant and visit. Only participants that show suicidal ideation/behavior or self-injurious behavior without suicidal intent will be displayed (i.e., if a participant answers are all 'no' for the C-SSRS, then that participant will not be displayed). However, if a participant reported any suicidal ideation/behavior or self-injurious behavior without suicidal intent at any time point then all their ideation and behavior will be displayed, even if not positive.

Suicidal ideation, suicidal behavior, and self-injurious behavior without suicidal intent occurring during treatment, based on the Columbia-Suicide Severity Rating Scale (C-SSRS), will be summarized by treatment. In particular, for each of the following events, the number and percent of participants with the event will be enumerated by treatment: completed suicide, nonfatal suicide attempt, interrupted attempt, aborted attempt, preparatory acts or behavior, active suicidal ideation with specific plan and intent, active suicidal ideation with some intent to act without specific plan, active suicidal ideation with any methods (no plan) without intent to act, nonspecific active suicidal thoughts, wish to be dead, and self-injurious behavior without suicidal intent. Although not suicide-related, the number and percent of participants with non-suicidal

self-injurious behavior occurring during the treatment period will also be summarized by treatment.

In addition, the number and percent of participants who experienced at least one of various composite measures during treatment will be presented and compared. These include suicidal behavior (completed suicide, non-fatal suicidal attempts, interrupted attempts, aborted attempts, and preparatory acts or behavior), suicidal ideation [active suicidal ideation with specific plan and intent, active suicidal ideation with some intent to act without specific plan, active suicidal ideation with any methods (no plan) without intent to act, non-specific active suicidal thoughts, and wish to be dead], and suicidal ideation or behavior.

The number and percent of participants who experienced at least one of various comparative measures during treatment will be presented and compared. These include treatment-emergent suicidal ideation compared to recent history, treatment-emergent serious suicidal ideation compared to recent history, emergence of serious suicidal ideation compared to recent history, improvement in suicidal ideation at endpoint compared to baseline, and emergence of suicidal behavior compared to all prior history.

Specifically, the following outcomes are C-SSRS categories and have binary responses (yes/no). The categories have been re-ordered from the actual scale to facilitate the definitions of the composite and comparative endpoints, and to enable clarity in the presentation of the results.

Category 1 – Wish to be Dead

Category 2 – Non-specific Active Suicidal Thoughts

Category 3 – Active Suicidal Ideation with Any Methods (Not Plan) without Intent to Act

Category 4 – Active Suicidal Ideation with Some Intent to Act, without Specific Plan

Category 5 – Active Suicidal Ideation with Specific Plan and Intent

Category 6 – Preparatory Acts or Behavior

Category 7 – Aborted Attempt

Category 8 – Interrupted Attempt

Category 9 – Actual Attempt (non-fatal)

Category 10 – Completed Suicide

Self-injurious behavior without suicidal intent is also a C-SSRS outcome (although not suicide-related) and has a binary response (yes/no).

Composite endpoints based on the above categories are defined below.

- Suicidal ideation: A “yes” answer at any time during treatment to any one of the five suicidal ideation questions (Categories 1-5) on the C-SSRS.
- Suicidal behavior: A “yes” answer at any time during treatment to any one of the five suicidal behavior questions (Categories 6-10) on the C-SSRS.
- Suicidal ideation or behavior: A “yes” answer at any time during treatment to any one of the ten suicidal ideation and behavior questions (Categories 1-10) on the C-SSRS.

Participants who discontinued from the study with no postbaseline C-SSRS value will be considered unevaluable for analyses of suicide-related events. Only evaluable participants will be considered in the analyses. Fisher's exact test will be used for treatment comparisons.

7.13.7.1.1. Columbia Suicide-Related Severity by Dose

For participants treated with solanezumab, summaries of suicidal ideation, suicidal behavior, and self-injurious behavior without suicidal intent occurring during treatment, based on the Columbia-Suicide Severity Rating Scale (C-SSRS), will be displayed with events assigned to the dose (400 mg versus 1600 mg for participants assigned to solanezumab, with events occurring at the 800-mg level assigned to the 1600-mg group, and low dose placebo and high dose placebo for participants assigned to placebo based on the blinded dose level) that the participant was taking at the time of the event. At the first occurrence of a high dose for a participant, all subsequent observations will also be considered as high dose.

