To date, no safety issues have been identified that would create an unfavorable benefit-risk balance for solanezumab. Few differences in the incidence of deaths, serious adverse events (SAEs), discontinuations due to adverse events (AEs), treatment-emergent adverse events (TEAEs), laboratory values, electrocardiograms (ECGs), treatment-emergent immunogenicity, treatment-emergent changes in amyloid-related imaging abnormalities (ARIA), and infusion reactions were observed between placebo- and solanezumab-treated subjects in the Phase 3 studies. In Studies LZAM and LZAN, a potential safety signal was identified for a heterogeneous set of cardiac-related events that included atrial fibrillation, bradycardia, and angina pectoris, reported in more than 1% but less than 2% of patients. The cardiac safety signal was not confirmed in Study LZAX and therefore is no longer considered a potential risk with solanezumab treatment. As measured by the Columbia Suicide Severity Rating Scale (C-SSRS), suicidal ideation and behaviors were infrequent, but a greater prevalence was observed among solanezumab- compared with placebo-treated mild AD dementia patients in Study LZAX. This

safety signal has not been observed in other solanezumab studies. At this time, it cannot be determined whether the imbalance observed in Study LZAX is causally related to solanezumab treatment. This safety signal will continue to be assessed in the ongoing A4 study. More details are available in the Investigator's Brochure (IB).

As described in the IB, 2 types of ARIA—hemosiderin deposition (ARIA-H, also known as cerebral microhemorrhage) and edema/effusions (ARIA-E, also known as vasogenic edema) and serious hypersensitivity reactions (immediate and nonimmediate) including anaphylaxis and infusion-related reactions—have been identified as potential risks for A β -based AD therapies. Magnetic resonance imaging (MRI) scans and AEs will be obtained in this study to assess these potential risks.

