9.1. Treatments Administered

This study was initiated as a comparison of solanezumab 400 mg compared with placebo. The active drug group was given an IV infusion of solanezumab 400 mg once every 4 weeks. The study protocol was amended to increase the dose; subjects will be escalated to 800 mg Q4W for at least 2 infusions, and then 1600 mg Q4W until the conclusion of the treatment, as described below (Table A4.1). Dosing should be once every 4 weeks; a minimum of 14 days between infusions is required.

Table A4.1. Treatment Regimens

Regimen	Dose from Visit 6 (Week 0) through Visit 65 (Week 236), Placebo-Controlled Period
Solanezumab	
 • 400 mg IV infusion every 4 weeks for at least 2 doses^a, and then: • 800 mg IV infusion every 4 weeks for at least 2 doses, and • 1600 mg IV infusion every 4 weeks through Week 236
Placebo	sterile saline solution (0.9% sodium chloride) IV infusion every 4 weeks (infusion volumes to increase accordingly with dose escalation paradigm as described in the operations manual)
Dose from Visit 66 (Week 240) through Visit 116 (Week 440), Open-Label Period	
Early-start solanezumab ^b	1600 mg IV infusion every 4 weeks through Week 440 ^c
Delayed-start solanezumab ^b	
 • 400 mg IV infusion every 4 weeks for at least 2 doses^{a, c}, • 800 mg IV infusion every 4 weeks for at least 2 doses^c, and • 1600 mg IV infusion every 4 weeks through Week 440^c

Abbreviation: IV = intravenous.

^a Subjects who initiated the study before the implementation of amendment (d) may have more than 2 doses of 400 mg Q4W.

^b “Early-start solanezumab” refers to the treatment regimen received by subjects randomized to solanezumab in the placebo-controlled period who continue to receive solanezumab in the open-label period. “Delayed-start solanezumab” refers to the treatment regimen received by subjects randomized to placebo in the placebo-controlled period who switch to solanezumab treatment in the open-label period.

^c Subjects who are receiving 400 mg Q4W or 800 mg Q4W when they complete the placebo-controlled period may be maintained at that dose in the open-label period.

Changes in the escalation schedule may be made at the investigator’s discretion with the notification of a Medical Monitor.

The investigator or his/her designee is responsible for the following:

- Explaining the correct use of the investigational agent(s) to the site personnel

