10.2.2. Columbia Suicide Severity Rating Scale

Consistent with FDA regulatory guidance (FDA 2012), any occurrence of suicide-related thoughts and behaviors will be assessed. The C-SSRS is a scale that captures the occurrence, severity, and frequency of suicide-related thoughts and behaviors during the corresponding assessment period. The scale includes suggested questions to elicit the type of information needed to determine if a suicide-related thought or behavior occurred.

The standard version of the scale will be used in this study. The first time the scale is administered in this study (Visit 1), the C-SSRS “Screening/Baseline” version will be used and the findings will be used to assist the clinician in determining eligibility. The C-SSRS will be administered at baseline (Visit 6) and at subsequent visits as outlined in the study schedule. The C-SSRS “Since Last Visit” scale will be used for baseline and all subsequent assessments.

If a suicide-related thought to behavior is identified at any time during the study, a thorough evaluation will be performed by a study physician, and appropriate medical care will be provided.

If, based on administration of the C-SSRS, it is determined that suicide-related behaviors have occurred, then the Lilly Self-Harm Follow-Up form will be used to collect additional information to allow for a more complete assessment.

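### In the C-SSRS summary by dose, the first assessment after escalation can look back up to 20 weeks on 400 mg yet is labelled high dose, and the SAP does not say how event time is set

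*SAP*

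**What the plan says.** SAP 7.13.7.1.1 gives two rules. The first assigns an event to the dose "that the participant was taking at the time of the event". The second reads: "At the first occurrence of a high dose for a participant, all subsequent observations will also be considered as high dose". High dose begins at the first 800 mg infusion, "with events occurring at the 800-mg level assigned to the 1600-mg group". Placebo is divided the same way, into "low dose placebo and high dose placebo for participants assigned to placebo based on the blinded dose level".

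Protocol 10.2.2 says that the scale "captures the occurrence, severity, and frequency of suicide-related thoughts and behaviors during the corresponding assessment period". The since-last-visit form of the "scale will be used for baseline and all subsequent assessments". Protocol Attachment 1 schedules it at Weeks 0 and 12, then every 24 weeks to Week 228, then at Week 240. SAP 7.13.7.1 treats each category as a yes/no response and lists results by participant and visit.

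Protocol Table A4.1 sets the start of the regimen: "400 mg IV infusion every 4 weeks for at least 2 doses". SAP 7.9.1.2.3 says that the timing of escalation varies between participants; neither document gives its distribution.

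**The concern.** The first rule needs the time of the event. A yes/no item covering the whole period since the previous assessment does not supply one, and neither document describes an onset date for it. Protocol 10.2.2 adds a self-harm form, but only for behaviors and not for ideation, and does not say that it records a date.

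For the first C-SSRS after escalation, the first rule may point to 400 mg while the second says high dose. Only the second can be applied with the data described, and it moves time in one direction: 400 mg look-back goes into the high-dose column, never the reverse.

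This table has a specific job. Protocol Section 5 reports an unexplained suicidality imbalance in the earlier mild-dementia study, which used 400 mg every 4 weeks, and says of it: "This safety signal will continue to be assessed in the ongoing A4 study". Protocol 11.2.13 asks for separate safety analyses of data on 400 mg and data on higher doses. The events were infrequent, so one or two in the wrong column could change how the table reads.

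**Working it through.** The plan states no figure for this summary, so there is nothing to reproduce. The check is arithmetic on the schedule of the placebo-controlled period.

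**Inputs**
- C-SSRS weeks (Attachment 1): 0, 12, 36, 60, 84, 108, 132, 156, 180, 204, 228, 240. The gaps are 12, nine of 24, then 12 weeks.
- Scales are done before the infusion (Protocol 9.5), so a C-SSRS on the escalation visit itself looks back on 400 mg only. I class it as low dose.
- Earliest first 800 mg infusion: Week 8, after 400 mg at Weeks 0 and 4.
- Possible first 800 mg visits: every 4 weeks from 8 to 236, which is (236 − 8)/4 + 1 = 58.

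**Formulas.** Let w be the week of the first 800 mg infusion and p the last C-SSRS week at or before w.
- Displaced 400 mg time: d = w − p
- Share of 400 mg time scored as high dose: d/w
- Share of high-labelled time that is 400 mg time: d/(240 − p)

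| w | p | d (weeks) | d/w | d/(240 − p) |
|---|---|---|---|---|
| 8 | 0 | 8 | 100% | 8/240 = 3% |
| 32 | 12 | 20 | 63% | 20/228 = 9% |
| 52 | 36 | 16 | 31% | 16/204 = 8% |
| 64 | 60 | 4 | 6% | 4/180 = 2% |
| 104 | 84 | 20 | 19% | 20/156 = 13% |
| 108 | 108 | 0 | 0% | 0% |
| 128 | 108 | 20 | 16% | 20/132 = 15% |
| 156 | 156 | 0 | 0% | 0% |

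**Results**
- Inside a 24-week window, d is 0, 4, 8, 12, 16 or 20 weeks, that is 0% to 83% of the window.
- Ten of the 58 possible visits fall on a C-SSRS visit (Weeks 12, 36, … 228). The other 48 give one straddling assessment.
- Over the 27 visits from Week 52 to Week 156, weighted equally, d sums to 276 weeks, a mean of 276/27 = 10.2. The mean of d/w is 11% and the mean of d/(240 − p) is 7%.
- On the minimum schedule the first post-baseline C-SSRS, at Week 12, covers 8 weeks on 400 mg and 4 weeks on 800 mg and is labelled high. That participant contributes no post-baseline 400 mg observation.
- With both ±10-day windows used in full, a 24-week look-back becomes 24 + 20/7 = 26.9 weeks. A missed assessment lengthens it further.

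**Direction of bias.** Raw high-dose counts can only rise. For rates per unit of look-back time, let f be the share of high-labelled time spent on 400 mg. The high-dose column then estimates f × (400 mg rate) + (1 − f) × (true high-dose rate). With equal true rates there is no bias. With f = 7% and a true ratio of 2, it estimates 0.07 × 1 + 0.93 × 2 = 1.93, slightly too low. If the true rate is lower on the high dose, the estimate is too high. Dividing the shifted counts by actual time on each dose would instead lower the 400 mg rate and raise the high-dose rate.

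**The case against.** The strongest reply is that the SAP does not assign by visit date. Its first rule is the dose at the time of the event, and a reader who sees only the second sentence might infer otherwise. That is right. The defect is that the plan does not say where event time comes from and does not reconcile the two sentences for one assessment. Nor do the documents show that onset is never recorded: the case report form is not among them, and Protocol 10.2.2 requires a physician evaluation after any positive finding. The fix allows for a recorded date.

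A reader might also infer that suicidality arising on 400 mg is counted as 1600 mg in general. It is not: at most one scheduled assessment per participant is involved. Nor does the table simply overstate the high dose; that holds for raw counts, while the direction in rates depends on the true rates and the denominator.

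Three further points stand. Placebo is split by the same rule, and the overall comparison in SAP 7.13.7.1, which is the one that matches the earlier signal against placebo, is untouched. Suicidality also reaches the plan as adverse events, with a cluster in SAP 7.13.1.4 and time-adjusted rates by dose in 7.13.1.3, though 7.13.7.1.1 is the only SAP section that shows the C-SSRS itself by dose. The parent section already gives number and percent among evaluable participants, so the by-dose table is not without any denominator; what it lacks is one that reflects observation on each dose.

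Finally, the last visit on the form could mean the last 4-weekly infusion visit, which would cut the look-back to about 4 weeks. The protocol's description of the recall period favors the longer reading, and the shorter one would leave the weeks between assessments uncovered.

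**Conclusion.** The point holds as a gap in the by-dose C-SSRS summary and is worth fixing. As described, event time cannot be set from the scale, and the rule that can be programmed places 0 to 20 weeks of 400 mg look-back in the high-dose column for one assessment per participant. The typical size is modest, about 11% of 400 mg time and 7% of high-labelled time. It is large only for early escalators, who may have no post-baseline 400 mg observation at all.

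The averages assume escalation spread evenly over the 4-weekly visits from Week 52 to Week 156, visits on schedule, same-day assessments classed as low dose, and a look-back to the previous C-SSRS. They are shares of time and carry over to events only if events arise evenly over time. What suffers is the contrast of 400 mg with higher doses within solanezumab. The documents do not support a claim that the randomized safety comparison is biased.

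**What to change.** In SAP 7.13.7.1.1:

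1. State how event time is determined. Use a recorded onset date where one exists.
2. Where there is none, assign a C-SSRS to a dose level only if its whole look-back was at that level. Show the first assessment whose look-back spans the escalation in a separate transition column, kept visible and not dropped.
3. State that a C-SSRS done before the first 800 mg infusion on the same day counts as low dose.
4. Report events per assessed interval, or per person-year of look-back, for each dose level in both arms. This brings the section into line with the time-adjusted approach of 7.13.1.3.

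The cost is SAP wording and programming, with no new data. The downside is that one assessment per participant leaves the two dose columns, and it is the one covering the start of the higher dose; the transition column keeps those events in view.
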